1.2 Study design

PS0041 is a Phase 3, multicenter, randomized, double blind, placebo controlled, parallel group study to evaluate the efficacy and safety of bimekizumab in Chinese adult study participants with moderate to severe plaque PSO.

The study population consists of Chinese adult study participants (≥ 18 years of age) with a diagnosis of moderate to severe plaque PSO (Baseline PASI ≥ 12 and Body Surface Area [BSA] affected by PSO $\geq 10\%$ and Investigator's Global Assessment [IGA] score ≥ 3 on a 5-point scale) who are candidates for systemic PSO therapy and/or phototherapy.

This study will include 4 periods: Screening Period (up to 5 weeks), Initial Treatment Period (16 weeks), Maintenance Treatment Period (16 weeks), and Safety Follow-Up (SFU) Period (17 weeks after the final dose of IMP [Figure 1-1]).

• Screening Period

The Screening Period will last up to a total of maximum 5 weeks (for example, in cases where a laboratory assessment needs to be repeated or to allow washout of prohibited medications). During the Screening Period, eligible study participants will be informed about the study and sign the Informed Consent Form (ICF). Following signed informed consent, all screening procedures and laboratory tests (hematology, urine, and biochemistry) will be performed per the Protocol Schedule of Activities (SoA). A study participant newly diagnosed with a latent TB infection (LTBI) as a result of a positive Interferon-Gamma Release Assay (IGRA) screening test, may be rescreened once and enrolled after receiving ≥ 4 weeks of appropriate LTBI therapy and after consultation with the Medical Monitor. Further details of rescreening are provided in the exclusion criteria in the Protocol.

After completion of the Screening Period, eligible study participants will be allowed to enroll into the study.

• Initial Treatment Period

During the 16-week Initial Treatment Period, approximately 120 Chinese adult study participants will be randomized 3:1 to receive the following blinded IMP regimens:

- Bimekizumab 320mg administered sc every 4 weeks (Q4W) (90 study participants)

-
- Placebo administered sc Q4W (30 study participants)

IMP will be administered in the clinic by sc injection at the visits specified in the Protocol SoA. Study participants withdrawing early from the study will undergo the premature end of treatment (PEOT) visit assessments and will enter the SFU period.

- Maintenance Treatment Period

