4.1.1.2 Analysis periods

The following study periods are defined:

- Screening Period: starts at the time of the informed consent date and ends one day before the first IMP administration.
- Initial Treatment Period (ITP): starts on the day of the first IMP administration and ends prior the first IMP administration in the maintenance treatment period (first IMP in the maintenance treatment period typically occurs at Week 16, but for those that miss the Week 16 IMP administration, first IMP in the maintenance treatment period will be the first IMP administration after Week 16). For study participants that withdraw from the study prior to start of IMP in the maintenance treatment period, the ITP ends on the day of the PEOT Visit. If the PEOT visit is not done, the ITP end date will be set to the date of premature study termination.
- Maintenance Treatment Period (MTP): starts on the day and time of the first IMP administration in the MTP (first IMP in the MTP typically occurs at Week 16 after all clinical and safety assessments have been completed, but for those who miss the Week 16 IMP administration, first IMP in the MTP will be the first IMP administration after Week 16) and ends at the Week 32 visit. For study participants withdrawn from the study after Week 16 but before Week 32, the MTP will end at the PEOT Visit. If the PEOT visit is not done, the MTP end date will be set to the date of premature study termination.
- SFU Period: for participant who complete the study, in other words, complete all scheduled visit, up to and including Week 32, the SFU period starts on the day after Week 32 and ends on the day of the SFU visit. For participants who withdraw early from the study the SFU period start on the day of after PEOT Visit and ends on the day of the SFU visit.

Study participants will be considered to have completed a period if they complete the last scheduled study visit including the respective assessments for that period. It is possible for a study participant to discontinue the study after the Week 16 visit without entering the MTP. Therefore, study participants who discontinue after Week 16 assessments and who never start the MTP will be counted as having completed the ITP but having discontinued the overall study. If study participants miss the Week 16 visit, but start treatment in the MTP, they will still be considered to have completed ITP.

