4.1.4 Treatment assignment and treatment groups

It is expected that study participants receive treatment as randomized for the ITP, or as assigned per protocol study design (via reallocation) for the MTP.

Safety analyses will be based on the SS, as randomized. However, if after unblinding it is determined that study participants randomized to placebo received bimekizumab at any time within the first 16 weeks, then for safety analyses these study participants will be reallocated to the appropriate bimekizumab treatment group, unless otherwise specified. Study participants randomized to bimekizumab will only be reallocated to the placebo treatment group if they never received bimekizumab.

Unless otherwise stated, the summary tables of safety analyses will be provided as:

- The ITP data will be displayed by Placebo and BZK 320mg Q4W columns based on the SS
- The MTP data will be displayed by BKZ 320mg Q4W and BKZ 320mg Q8W columns based on the MS by treatment received at the MTP
- The initial and maintenance treatment period data will be displayed by BKZ 320mg Q4W, BKZ 320mg Q8W, and BKZ 320mg Total columns based on the AMS

Study participants randomized to BKZ 320mg Q4W and received BKZ 320mg Q8W in the MTP will be represented in both the BKZ 320mg Q4W and BKZ 320mg Q8W treatment columns. BKZ 320mg Q8W column only presents the data after the switch from BZK 320mg Q4W to BKZ 320mg Q8W. BKZ 320mg Q4W column will also include study participants that switch from Placebo to BKZ 320mg Q4W (only data after switch).

Efficacy analyses should be performed according to randomized treatment and not actual treatment received.

Unless otherwise stated, the summary tables of efficacy analyses will be provided as:

- The ITP data will be displayed by Placebo and BZK 320mg Q4W columns based on the RS
- The MTP data will be displayed by BKZ 320mg Q4W column and BKZ 320mg Q8W column based on the MS by treatment received at the MTP
- The initial and maintenance treatment period data will be displayed by Placebo/BKZ 320mg Q4W and BZK 320mg Q4W/Q8W columns based on the randomized treatment sequence by RS

For all TFLs for demographics, baseline disease characteristics, previous and ongoing medical history, prior and concomitant medications, and psoriasis treatment history, the summary will be displayed by Placebo/BKZ 320mg Q4W and BKZ 320mg Q4W/Q8W columns based on the randomized treatment sequence.

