4.5.1.1 Exposure during the ITP

Definitions for study medication duration (days) and time at risk (days) during the ITP are provided as follows:

Study medication duration (days)

Date of last dose in the ITP – date of first dose in the ITP + 28

The use of +28 reflects the dosing interval of Q4W.

- If the date of last dose in the ITP + 28 days extends to a date beyond the date of first dose of the MTP, then this calculation reverts to:

Date of first dose in the MTP – date of first dose in the ITP + 1

- For study participants who died during the ITP, if date of last dose in the ITP + 28 days extends beyond the date of death, then this calculation reverts to:

Date of death – date of first dose in the ITP + 1

- For study participants who discontinue the ITP early, if date of last dose in the ITP + 28 days extends beyond the date of the last visit (including PEOT, not including SFU), then this calculation reverts to:
 - *Date of last visit – date of first dose in the ITP + 1*

Time at risk (days)

For study participants who complete the final visit of the ITP (Week 16 visit) and continue to the MTP:

$$\text{Date of first dose in the MTP} - \text{date of first dose in the ITP} + 1$$

For study participants who died during the ITP:

$$\text{Date of death} - \text{date of first dose in the ITP} + 1$$

For study participants who discontinue the ITP early or who complete the ITP but not continue to the MTP, use the minimum of the following:

- *The total number of days in the ITP (112 days). For AEs that emerged after 112 days but still within the 119 days window, those AEs would be classified as TEAE, but will be excluded from the output based on the ITP. However, these AEs will be included in the AE summaries for Initial and Maintenance Treatment Period (combined).*
- *Date of last clinical contact – date of first dose in the ITP + 1*

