4.5.1.2 Exposure during the MTP

Definitions for study medication duration (days) and time at risk (days) during the MTP are provided as follows:

Study medication duration (days)

$$\text{Date of last active dose in the MTP} - \text{date of first dose in the MTP} + 28$$

The use of 28 days assumes a Q4W dosing interval. This will be adjusted based on the dosing interval (eg, for Q8W use Date of last active dose in the MTP – date of first dose in the MTP + 56 days).

- If the date of last active dose in the MTP + 28 days (or 56 days in the case of Q8W dosing) extends to a date beyond the date of last visit in the MTP (including PEOT, not including SFU), then this calculation reverts to:

$$\text{Date of last visit in the MTP} - \text{date of first dose in the MTP} + 1$$

- For study participants who died during the MTP, if date of last active dose in the MTP + 28 days (or 56 days in the case of Q8W dosing) extends beyond the date of death, then this calculation reverts to:

$$\text{Date of death} - \text{date of first dose in the MTP} + 1$$

Time at risk (days)

For study participants who died during the MTP:

$$\text{Date of death} - \text{date of first dose in the MTP} + 1$$

For study participants who complete the MTP (not including SFU) as scheduled or who discontinue the MTP early, use the minimum of the following:

- $\text{Date of last dose in the MTP} - \text{Date of first dose in the MTP} + 119$
- $\text{Date of last clinical contact} - \text{date of first dose in the MTP} + 1$

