4.5.1.3 Exposure during the Initial and Maintenance Treatment Period (combined)

Definitions for study medication duration (days) and time at risk (days) during the Initial and Maintenance Treatment Period (combined) are provided as follows:

Study medication duration (days)

Study medication duration will be summarized for BKZ 320mg Q4W, BKZ 320mg Q8W, and BKZ 320mg Total respectively:

- For BKZ 320mg Q4W:

Include study medication duration in ITP for study participants who are randomized to BKZ 320mg Q4W in ITP (refer to section 4.5.1.1 – study medication duration) and study medication duration in MTP for study participants who are randomized to placebo in ITP and switch to BKZ 320mg Q4W in MTP (refer to section 4.5.1.2 – study medication duration)

- For BKZ 320mg Q8W:

Include study medication duration in MTP for study participants who switch to BKZ 320mg Q8W in MTP (refer to section 4.5.1.2 – study medication duration)

- For BKZ 320mg Total:

For study participants randomized to BKZ 320mg Q4W in the ITP:

$\text{Date of last active dose} - \text{date of first dose in the ITP} + 28$ (if last active dose was in the ITP) or 56 (if last active dose was in the MTP)

- If the date of last active dose + 28 days (if last active dose was in the ITP) or 56 days (if last active dose was in the MTP) extends to a date beyond the date of last visit (including PEOT, not including SFU), then this calculation reverts to:

$\text{Date of last visit} - \text{date of first dose in the ITP} + 1$

- For study participants who died, if date of last active dose + 28 days (if last active dose was in the ITP) or 56 days (if last active dose was in the MTP) extends beyond the date of death, then this calculation reverts to:

$\text{Date of death} - \text{date of first dose in the ITP} + 1$

For study participants randomized to Placebo in ITP and switch to BKZ 320mg Q4W in MTP:

Include study medication duration in MTP defined in section 4.5.1.2 – study medication duration.

Time at risk (days)

Time at risk will be summarized for BKZ 320mg Q4W, BKZ 320mg Q8W, and BKZ 320mg Total respectively:

- For BKZ 320mg Q4W:

For study participants who are randomized to BKZ 320mg Q4W in ITP:

- For study participants who complete the final visit of the ITP (Week 16 visit) and continue to the MTP

Date of first dose in the MTP – date of first dose in the ITP + 1

- For study participants who died during the ITP

Date of death – date of first dose in the ITP + 1

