- For study participants who discontinue the ITP early or who complete the ITP but do not continue to the MTP, use the minimum of the following:

Date of last dose in the ITP – Date of first dose in the ITP + 119

Date of last clinical contact – date of first dose in the ITP + 1

For study participants who are randomized to placebo in ITP and switch to BKZ 320mg Q4W in MTP:

Include time at risk in MTP defined in section 4.5.1.2 – time at risk.

- For BKZ 320mg Q8W:

Include time at risk in MTP for study participants who switch to BKZ 320mg Q8W in MTP (refer to section 4.5.1.2 – time at risk).

- For BKZ 320mg Total:

For study participants randomized to BKZ 320mg Q4W in ITP:

- For study participants who died before the final visit (not including SFU):

Date of death – date of first dose in the ITP + 1

- For all the other study participants including who discontinue early or who complete the MTP as scheduled, use the minimum of the following:

Date of last dose – Date of first dose in the ITP + 119

Date of last clinical contact – date of first dose in the ITP + 1

For study participants who are randomized to Placebo in ITP and switch to BKZ 320mg Q4W in MTP:

Include time at risk in MTP defined in section 4.5.1.2 – time at risk

A by-study participant listing of exposure to study medications will be provided on the SS by treatment group.

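### In the combined-period safety tables, about 45% of Q8W but 17% of Q4W person-time falls after Week 32, so event rates per participant-year in the two columns are not like for like

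*SAP*

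**What the plan says.** **Combined tables (SAP 4.5.1.3, on the AMS).** Three rules matter for participants who go through the schedule.

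- Participants randomized to bimekizumab who continue after Week 16 contribute to the Q4W column "Date of first dose in the MTP – date of first dose in the ITP + 1", so their Q4W clock stops at the first maintenance dose.
- Placebo participants join the Q4W column after the switch (SAP 4.1.4: "BKZ 320mg Q4W column will also include study participants that switch from Placebo to BKZ 320mg Q4W (only data after switch") and carry the maintenance time at risk.
- For the Q8W column the instruction is "Include time at risk in MTP for study participants who switch to BKZ 320mg Q8W in MTP".

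**Maintenance rule (SAP 4.5.1.2).** A death during the MTP ends time at risk on that date. For the rest: "For study participants who complete the MTP (not including SFU) as scheduled or who discontinue the MTP early, use the minimum of the following". The two candidates are the last MTP dose minus the first MTP dose plus 119 days, and the date of last clinical contact. SAP 4.1 counts placebo injections in the MTP as IMP, so for a Q8W completer the last dose is the Week 28 injection.

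**Periods and events.** The MTP definition in SAP 4.1.1.2 reads "will be the first IMP administration after Week 16) and ends at the Week 32 visit", and the SFU period starts the day after. SAP 4.5.2.1 counts TEAEs up to 119 days after the final dose, and SAP 4.5.2.2 assigns them to tables by the time-at-risk windows of 4.5.1. The ITP tables are handled differently: participants who do not continue are capped at 112 days, and for later events "those AEs would be classified as TEAE, but will be excluded from the output based on the ITP".

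**The concern.** The combined tables put Q4W and Q8W side by side as rates per 100 participant-years: the exposure-adjusted incidence rate (EAIR) and event rate (EAER). The Q8W column has a long post-treatment tail for every completer. The Q4W column has one only for placebo switchers and for bimekizumab starters who do not continue. The columns therefore mix time on treatment and time after it in different proportions.

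The Schedule of Activities has no visit between Week 32 and the SFU Visit about 13 weeks later, so fewer events may be reported in that stretch. If so, Q8W would show lower rates than Q4W even with identical rates on treatment.

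The combined tables also carry most of the safety content for Q8W. Serious TEAEs, TEAEs leading to discontinuation and the safety topics of interest are planned only for the ITP and the combined period (SAP 4.5.2.2 and 4.5.2.4). For these, the combined table is the only place where a Q8W rate appears.

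**Working it through.** **Inputs.** 90 participants start on bimekizumab and 30 on placebo (SAP 1.2). Dosing visits are Baseline and Weeks 4, 8, 12, 16, 20, 24 and 28 (SAP 6.11). The plan's 119 days reproduce as 17 × 7, and its 112-day ITP as 16 × 7. Nominal visit days are used and everyone completes, unless stated.

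**Days per completer**
- Q4W, bimekizumab starter: 112 + 1 = 113, with no tail.
- Q8W: Week 16 to Week 28 is 84 days; 84 + 119 = 203. Week 16 to Week 32 is 112, so 203 − 112 = 91 days follow Week 32.
- Q4W, placebo switcher: also 203, of which 91 follow Week 32.

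**Column totals**
- Q8W: 90 × 203 = 18,270 days (÷ 365.25 = 50.0 participant-years). After Week 32: 90 × 91 = 8,190, or 44.8%.
- Q4W: 90 × 113 + 30 × 203 = 16,260 days (44.5 participant-years). After Week 32: 30 × 91 = 2,730, or 16.8%.
- Bimekizumab starters, who have no tail, are 90/120 = 75% of people in the Q4W column and 10,170/16,260 = 62.5% of its time.
- With 5% or 10% ITP dropout (assumed, last dose at Week 8), the Q4W share after treatment rises to 18.5% or 20.2%. The Q8W share stays at 44.8%.

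**Effect on the EAER.** Let both regimens have the same on-treatment rate, and let the rate after Week 32 be r times that rate. The documents do not give r, so a range is shown.

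Q8W/Q4W = [(112 + 91r)/203] ÷ [(10,170 + 30 × (112 + 91r))/16,260]

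| r | Q8W factor | Q4W factor | Ratio |
|---|---|---|---|
| 0 | 0.552 | 0.832 | 0.66 |
| 0.25 | 0.664 | 0.874 | 0.76 |
| 0.50 | 0.776 | 0.916 | 0.85 |
| 0.75 | 0.888 | 0.958 | 0.93 |
| 1 | 1.000 | 1.000 | 1.00 |
| 1.25 | 1.112 | 1.042 | 1.07 |

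**Effect on the EAIR**, where time stops at the first event (constant hazards assumed). At on-treatment rates of 5, 50 and 200 per 100 participant-years, the ratio is 0.66, 0.68 and 0.72 at r = 0. At r = 0.5 it is about 0.85, 0.86 and 0.88.

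**Where r is near zero by schedule.** No IMP is given at Week 32, so a completer has nothing left to discontinue. Acute anaphylaxis must start on an injection day or the day after (SAP 4.5.2.4.7). New injection site reactions are unlikely months after the last injection. As a cross-check, count dosing visits and assume equal risk at each, active or placebo. Q8W has 90 × 4 = 360 over 18,270 days and Q4W has 120 × 4 = 480 over 16,260 days. The ratio is (360/18,270) ÷ (480/16,260) = 0.67, in line with the 0.66 in the table.

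**Percentages of participants.** Longer observation pushes these the other way. At r = 0.5 and 50 per 100 participant-years, 19.4% of Q8W and 15.6% of Q4W participants would have an event. At r = 0 the two are almost equal (14.2% and 14.3%).

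**The case against.** A reader might infer that Q8W rates are simply diluted. The documents do not support that. Events in the tail are counted in the numerator, so a distortion needs a lower event rate there, and neither document gives one. Protocol 8.5 has monitoring after an overdose run until bimekizumab is no longer detectable, at 90 days or more, so the weeks after Week 32 are not plainly free of drug. At equal rates there is no distortion, and at a higher rate it reverses.

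Three other strong readings also fail.

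- That every Q8W participant carries the full tail. Deaths stop at death, others stop at an earlier last contact, and at the primary analysis after Week 32 the tail is incomplete for later enrollees.
- That 147 of the 203 days are off treatment. That is the time after the last active dose at Week 24, but 56 of those days are the planned Q8W interval. The part after the treatment period is 91 days, the same as for a placebo switcher.
- That the MTP tables contradict the SAP's own period definition. SAP 4.5.2.2 expressly sends event attribution to the 4.5.1 windows. In those tables both regimens follow one rule, so a fair comparison exists for the TEAE overview and for all TEAEs by SOC, HLT and PT.

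The rules also look deliberate: the SAP version history ties the exposure definitions to the global pivotal studies. The combined columns are descriptive, with risk differences planned only for the ITP. The same 90 people appear in both columns at different times, which confounds any Q4W/Q8W reading however the tail is handled. Giving continuing participants a Q4W tail would be wrong too, since they are then on Q8W.

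All of this stands. It does not remove the unequal mix in the combined tables, the near-zero tail rate for dosing-tied events, or the lack of an MTP version for serious TEAEs, discontinuations and safety topics.

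**Conclusion.** The point holds for the combined tables on the AMS, and only there. At planned sizes with all completing, 44.8% of Q8W and 16.8% of Q4W person-time falls after Week 32.

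For adverse events in general the consequence is conditional. Under equal on-treatment rates the Q8W/Q4W ratio is 0.93, 0.85 or 0.76 at assumed relative tail rates of 0.75, 0.50 or 0.25, and 1.00 if rates do not change. For TEAEs leading to IMP discontinuation, acute anaphylaxis and injection site reactions, the schedule alone puts the ratio near 0.66, a reading about one third too low. In the same table the percentages can point the other way.

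These figures rest on nominal visit days, the planned 90 and 30 participants, full completion and a complete tail, so they describe the final analysis rather than the one after Week 32. The remedy is a cheap improvement in how these rates are presented. Replacing the 119-day rule would trade away consistency with the global studies, and the finding does not require it.

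**What to change.** Keep the 119-day rule and the existing tables. In SAP 4.5.1.3 and 4.5.2.2, add for the Q4W and Q8W columns of the combined tables a set of EAIR and EAER in which both events and time at risk end with the treatment period as SAP 4.1.1.2 defines it. That is the first MTP dose for bimekizumab starters in the Q4W column who continue, and the Week 32 or PEOT visit otherwise. Show events and person-time after that point in a separate row or column by last regimen.

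With 113 days per completer in each column, Q8W has 90 × 113 = 10,170 days (27.8 participant-years, against 50.0 now) and Q4W has 120 × 113 = 13,560 days (37.1, against 44.5). The ratio under equal on-treatment rates is then 1.00 whatever the tail rate.

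The cost is SAP wording and one extra set of rates, with wider EAIR intervals because the person-time is shorter. No event is lost, since later ones appear in the separate row and in the existing tables. The confounding of regimen with time since first dose remains.
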